#### **Motor Function (Upper Arm): Performance of Upper Limb (PUL) [Middle Level Elbow Dimension] – (BB Muscle Group)**

Individual data will be listed.

Descriptive statistics will be provided by treatment group for those receiving study drug in the biceps brachii muscle for the following components from the mid-level PUL:

- Composite (or average) of time to complete the four timed tasks from the mid-level PUL
- Time to lift 5 light cans
- Time to stack 5 light cans
- Time to lift 5 heavy cans
- Time to stack 5 heavy cans
- Mid-level elbow dimension total score

For the composite (or average) of times to complete the four timed tasks from the mid-level PUL, an ANCOVA model will be fitted in order to assess the effect of ACE-083 on the Day 190 percent change from baseline data. Covariates to be included in the model are TREATMENT, MRC-MMT GRADE CATEGORY, and BASELINE where BASELINE represents the baseline

PUL composite time and each of the other covariates are defined the same as what was done for the primary analysis.

The effect of ACE-083 on the Day 190 percent change in the mid-level PUL composite time from baseline versus placebo will be estimated using the ANCOVA model described above and tested using a 0.1 significance level (2-sided). The least-squares mean estimate along with the corresponding 90% confidence interval will be provided. In addition, the 95% confidence interval will also be provided as well as a bar chart of the least squares mean estimates ( $\pm$  SEM) for each of the treatment groups.

A mixed model repeated measures (MMRM) analysis will be performed to assess the sensitivity to the ANCOVA analysis described above. An unstructured covariance structure will be used to model the within-patient covariance across visits. Other covariance structures will be considered if the unstructured covariance fails. The covariates to be included consist of all of the covariates described above for the ANCOVA with the addition of the following additional covariates: VISIT where VISIT represents the scheduled visit day post first dose of MRI assessment and TREATMENT\*VISIT.

For both the ANCOVA and MMRM analyses, multiple imputations will be performed for missing data. Twenty imputations will be performed. The seed to be used is specified in [Section 6](#). The assumption of the missing data mechanism will be missing at random (MAR) unless the data suggest otherwise. The missing data pattern (monotone or arbitrary) will also be evaluated and the regression method for imputing missing data will be utilized for each scheduled timepoint with missing data. Covariates to be included when imputing missing data include: MRC-MMT GRADE CATEGORY, TREATMENT, BASELINE, and PUL percent change data at scheduled timepoints prior to the timepoint at which PUL percent change is being imputed.

The table below illustrates the covariates that should be used for imputing missing data for selected timepoints:

Data to be imputed	Covariates to use in multiple imputation regression model
Baseline PUL	MRC-MMT GRADE CATEGORY, TREATMENT
Day 22 percent change in PUL from baseline	MRC-MMT GRADE CATEGORY, TREATMENT, BASELINE
Day 43 percent change in PUL from baseline	MRC-MMT GRADE CATEGORY, TREATMENT, BASELINE, Day 22 PUL percent change
Day 190 Percent change in PUL from baseline	MRC-MMT GRADE CATEGORY, TREATMENT, BASELINE, Days 22, 43, 64, 85, 106, 148, and 169 PUL percent change from baseline

Note: PUL means either the composite (mean) time to perform the 4 timed activities or the PUL mid-level dimension score.

Analysis findings will be presented for Day 190 percent change data where missing data is not imputed (observed data) as well as for Day 190 percent change data where multiple imputations are performed for missing data to assess the impact of the missing data on the observed study data. The analyses where multiple imputations are performed are considered to be primary.

The analyses described above will also be performed for the mid-level PUL dimension score.

The Per Protocol Set will be used for the primary analysis. The analyses described above will also be repeated for the Full Analysis Set.

Additional analyses may be performed as appropriate.

#### **Motor function (upper arm): Performance of upper limb (PUL) [Upper level dimension] – (BB muscle group)**

Individual data will be listed.

The number and percentage of subjects of weight used to perform each of the four components of the PUL upper level dimension (shoulder domain) will be presented by treatment group and scheduled time. The four components are:

- Shoulder abduction to shoulder height (elbow to shoulder level)
- Shoulder abduction above shoulder height (elbow to eye level)
- Shoulder flexion to shoulder height (elbow to shoulder level)
- Shoulder flexion above shoulder height (elbow to eye level)

Descriptive statistics will be provided by scheduled time for the raw PUL shoulder domain score (average PUL shoulder domain score of left and right sides) and changes from baseline (absolute and percent change) by treatment group sequence in the open-label phase of Part 2.

Additional analyses may be performed as appropriate.

#### **Patient Reported Outcomes: Facioscapulohumeral Disease Health Index (FSHD-HI) Survey**

Individual FSHD-HI scored data (total score and each of the subscale scores) will be listed.

Descriptive statistics of the raw data as well as for the absolute and percent change from baseline will be provided for the FSHD-HI total score as well as for each of the subscale scores.

Least square mean estimates of the effect of ACE-083 and corresponding 90% and 95% confidence intervals will be produced for the Day 190 absolute change data described above using an ANCOVA with MUSCLE, BASELINE, TREATMENT MRC-MMT GRADE CATEGORY, and MUSCLE\*TREATMENT as covariates where MUSCLE, BASELINE, TREATMENT, and MRC-MMT GRADE CATEGORY are defined similarly as described above for other analyses. In addition, a bar chart of the least squares mean estimates ( $\pm$  SEM) by muscle for each of the treatment groups will be provided for the following FSHD-HI parameters: FSHD-HI total score, FSHD-HI Arm/Shoulder function (BB only), FSHD-HI Mobility (TA only), and FSHD-HI Activity limitation.

A mixed model repeated measures (MMRM) analysis will be performed to assess the sensitivity to the ANCOVA analysis described above. An unstructured covariance structure will be used to

model the within-patient covariance across visits. Other covariance structures will be considered if the unstructured covariance fails. The covariates to be included consist of all of the covariates described above for the ANCOVA with the addition of the following additional covariates: VISIT where VISIT represents the scheduled visit day post first dose assessment, MUSCLE\*VISIT, TREATMENT\*VISIT, and MUSCLE\*TREATMENT\*VISIT.

For both the ANCOVA and MMRM analyses, multiple imputations will be performed for missing data. Twenty imputations will be performed. Imputations will be performed separately for the BB and TA patients. The seed to be used is specified in [Section 6](#). The assumption of the missing data mechanism will be missing at random (MAR) unless the data suggest otherwise. The missing data pattern (monotone or arbitrary) will also be evaluated and the regression method for imputing missing data will be utilized for each scheduled timepoint with missing data. Covariates to be included when imputing missing data include: MRC-MMT GRADE CATEGORY, TREATMENT, BASELINE and FSHD-HI absolute change data at scheduled timepoints prior to the timepoint at which FSHD-HI absolute change is being imputed.

The table below illustrates the covariates that should be used for imputing missing data:

Data to be imputed	Covariates to use in multiple imputation regression model
Baseline FSHD-HI	MRC-MMT GRADE CATEGORY, TREATMENT
Day 22 absolute change from baseline	MRC-MMT GRADE CATEGORY, TREATMENT, BASELINE
Day 43 absolute change from baseline	MRC-MMT GRADE CATEGORY, TREATMENT, BASELINE, Day 22 FSHD-HI absolute change
Day 190 absolute change from baseline	MRC-MMT GRADE CATEGORY, TREATMENT, BASELINE, Days 22, 43, 64, 85, 106, and 148 FSHD-HI absolute change

Analysis findings will be presented for Day 190 percent change data where missing data is not imputed (observed data) as well as for Day 190 percent change data where multiple imputations are performed for missing data to assess the impact of the missing data on the observed study data. The analyses where multiple imputations are performed are considered to be primary.

The Per Protocol Set will be used for the primary analysis. The analyses described above will also be repeated for the Full Analysis Set.

Additional analyses may be performed as appropriate.

### Gait

Individual data will be listed.

Descriptive statistics will be provided for each type of measurement recorded (e.g., “General measures”, “Initial measures”, “Peak measures”, and “Average measures”) by treatment group and scheduled time.

For gait assessments that are reported in triplicates at a given visit for any patient and are assessed to be of good quality, the mean of these will be used for purposes of generating a single individual value for the patient at the scheduled visit which will then be summarized.

In addition, “Stride Length” will be derived using the following formula:

Stride Length (m) = {Mean of the triplicate measures of Left Step Length (m)} + {Mean of the triplicate measures of Right Step Length (m)}

Additional analyses may be performed as appropriate.

No imputations will be performed for missing gait data.

#### **4.7.2.3. Part 2 Open-Label Extension**

Individual data will be listed. The listing of such data will be collated with the data collected in the double-blind, placebo-controlled phase.

Descriptive statistics will be provided for raw data and changes (percent and absolute change) from the start of the open-label extension (Day 190) will be provided by treatment sequence for each scheduled time. The treatment sequence refers to the treatment sequence from double-blind to open label (i.e. ACE-083 □ ACE-083 or Placebo □ ACE-083). For MRI and strength data, such summaries will be provided by scheduled time for each side treated as well as the average of the left and right sides.

Additional analyses may be performed as appropriate.

#### **Open-Label Extension vs. Double-Blind Placebo-Controlled Phase**

#### **Selected MRI, and FSHD-HI Total Score and FSHD-HI Activity Limitation Subscale Score**

For total muscle volume, calculated contractile muscle volume, fat fraction, FSHD-HI total score, and FSHD-HI activity limitation subscale score, descriptive statistics will be provided for the Placebo □ ACE-083 treatment sequence for the difference in percent (or absolute) change observed between Day 190 and pre-first treatment baseline (1st 6 months) and the percent (or absolute) change observed between Day 358 and the open-label treatment baseline (2nd 6 months).

In addition, the effect of ACE-083 administered during the open-label extension compared to the treatment administered in the double-blind placebo-controlled phase will be examined for those receiving ACE-083 during the double-blind phase and separately for those receiving placebo during the double-blind phase by comparing the percent (or absolute) change observed between Day 190 and pre-first treatment baseline (1st 6 months) and Day 358 versus the open-label treatment baseline (2nd 6 months) using an ANCOVA model for each individual data parameter.

Covariates to be included into the model are MUSCLE, SEQUENCE, MRC-MMT GRADE CATEGORY, BASELINE, and MUSCLE\*SEQUENCE where:

- MUSCLE refers to the muscle treated (i.e. BB or TA)
- SEQUENCE refers to the treatment sequence from double-blind to open-label (ACE-083 □ ACE-083 or Placebo □ ACE-083)

- MRC-MMT GRADE CATEGORY refers to the randomization stratification factor from the double-blind phase
- BASELINE refers to baseline from the double-blind phase
- MUSCLE\*SEQUENCE refers to the muscle-by-sequence interaction

Least squares estimates of the SEQUENCE\*MUSCLE effect and the corresponding 90% confidence interval will be provided and will be tested using a 0.1 significance level (2-sided). In addition, the least squares estimates for each sequence along with the corresponding 90% confidence interval will be provided separately for each muscle and will be tested using a 0.1 significance level (2-sided).

Multiple imputations will be performed for missing data. Twenty imputations will be performed. The seed to be used is specified in [Section 6](#). The assumption of the missing data mechanism will be missing at random (MAR) unless the data suggest otherwise. The missing data pattern (monotone or arbitrary) will also be evaluated and the regression method for imputing missing data will be utilized for each scheduled timepoint with missing data. Covariates to be included when imputing missing data include: MRC-MMT GRADE CATEGORY, MUSCLE, SEQUENCE, BASELINE, MUSCLE\*SEQUENCE, and percent (or absolute change) of the analysis variable at scheduled timepoints prior to the timepoint at which the analysis variable percent (or absolute) change is being imputed.

Analysis findings will be presented where missing data is not imputed (observed data) as well as for the case where multiple imputations are performed for missing data to assess the impact of the missing data on the observed study data. The analyses where multiple imputations are performed are considered to be primary.

The Per Protocol Set will be used for the primary analysis. The analyses described above will also be repeated for the Full Analysis Set.

Additional analyses may be performed as appropriate.

#### **Selected Motor Function, FSHD-HI Arm/Shoulder Function Subscale Score, MVIC, MRC-MMT Score, FSHD-HI Mobility and Ambulation Subscale Score**

For mid-level PUL composite time (BB patients only), 6MWD (TA patients only), time to complete the 10mW/R (TA patients only), 4-stair climb ascend time (TA patients only), 4-stair descend time (TA patients only), FSHD-HI arm/shoulder function subscale score (BB patients only), FSHD-HI mobility and ambulation subscale score (TA patients only), MVIC (elbow flexion – BB patients), MVIC (ankle dorsiflexion – TA patients), MRC-MMT score (elbow flexion – BB patients), MRC-MMT score (ankle dorsiflexion – TA patients), descriptive statistics will be provided for the Placebo □ ACE-083 treatment sequence for the difference in percent (or absolute) change observed between Day 190 and pre-first treatment baseline (1st 6 months) and the percent (or absolute) change observed between Day 358 and the open-label treatment baseline (2nd 6 months).

In addition, the effect of ACE-083 administered during the open-label extension compared to the treatment administered in the double-blind placebo-controlled phase will be examined for those receiving ACE-083 during the double-blind phase and separately for those receiving placebo during the double-blind phase by comparing the percent (or absolute) change observed between

Day 190 and pre-first treatment baseline (1st 6 months) and Day 358 versus open-label treatment baseline (2nd 6 months) using an ANCOVA model for each individual data parameter.

Covariates to be included into the model are SEQUENCE, MRC-MMT GRADE CATEGORY, HEIGHT (only for 6MWD and 10mW/R) and BASELINE where:

- SEQUENCE refers to the treatment sequence from double-blind to open-label (ACE-083 □ ACE-083 or Placebo □ ACE-083)
- MRC-MMT GRADE CATEGORY refers to the randomization stratification factor from the double-blind phase
- BASELINE refers to baseline from the double-blind phase
- HEIGHT refers to the patient's height (cm)

Least squares estimates for each sequence and 90% confidence intervals will be provided and will be tested using a 0.1 significance level (2-sided).

Multiple imputations will be performed for missing data. Twenty imputations will be performed. The seed to be used is specified in [Section 6](#). The assumption of the missing data mechanism will be missing at random (MAR) unless the data suggest otherwise. The missing data pattern (monotone or arbitrary) will also be evaluated and the regression method for imputing missing data will be utilized for each scheduled timepoint with missing data. Covariates to be included when imputing missing data include: MRC-MMT GRADE CATEGORY, SEQUENCE, BASELINE, HEIGHT (only for 6MWD and 10mW/R) and percent (or absolute change) of the analysis variable at scheduled timepoints prior to the timepoint at which the analysis variable percent (or absolute) change is being imputed.

Analysis findings will be presented where missing data is not imputed (observed data) as well as for the case where multiple imputations are performed for missing data to assess the impact of the missing data on the observed study data. The analyses where multiple imputations are performed are considered to be primary.

The Per Protocol Set will be used for the primary analysis. The analyses described above will also be repeated for the Full Analysis Set.

Additional analyses may be performed as appropriate.

#### 4.7.2.4. Subgroup Analyses (Part 2 Only)

Subgroups consist of the following:

- D4Z4 fragment size (< 23 kb; ≥ 23 kb)
- Dose per Calculated Contractile Muscle Mass (mg/g)
  - BB: (< 2.9; ≥ 2.9); TA: (< 3.5; ≥ 3.5)
- Exercise Program: (Some; None)
- Baseline FSHD-HI Total Score:
  - BB: (< median; ≥ median); TA: (< median; ≥ median)

Note that the median will be the median of the average of the FSHD-HI total score for the assessments performed at Screening Days -28 and -7 and Day 1 and will be determined separately for BB and TA patients.

- Baseline Fat Fraction (%)
  - BB: (< median;  $\geq$  median); TA: (< median;  $\geq$  median)

Note that the median will be determined separately for BB and TA patients.

- Knee Extension MRC-MMT Grade {weaker of two sides – TA patients only}
  - (2- to 4-; 4 to 5)
- Elbow Flexion MRC-MMT Grade {weaker of two sides – BB patients only}
  - (3 to 4-; 4 to 4+)
- Ankle Dorsiflexion MRC-MMT Grade {weaker of two sides – TA patients only}
  - (3 to 4-; 4 to 4+)

Subgroup analyses will be performed for the following parameters:

- Day 190 average percent change in total muscle volume from baseline
- Day 190 average percent change in calculated contractile muscle volume from baseline
- Day 190 average absolute change in fat fraction from baseline
- Day 190 average percent change in fat fraction from baseline
- Day 190 average percent change in elbow flexion MVIC from baseline
  - To be done for all subgroups above with the exception of “Knee Extension MRC-MMT Grade” and “Ankle Dorsiflexion MRC-MMT Grade” subgroups
- Day 190 average percent change in ankle dorsiflexion MVIC from baseline
  - To be done for all subgroups above with the exception of “Elbow Flexion MRC-MMT Grade”
- Day 190 percent change in 6MWD from baseline
  - To be done for all subgroups above with the exception of “Elbow Flexion MRC-MMT Grade”
- Day 190 percent change in time to complete 10mW/R from baseline
  - To be done for all subgroups above with the exception of “Elbow Flexion MRC-MMT Grade”
- Day 190 percent change in PUL composite time from baseline
  - To be done for all subgroups above with the exception of “Knee Extension MRC-MMT Grade” and “Ankle Dorsiflexion MRC-MMT Grade” subgroups
- Day 190 absolute change in FSHD-HI total score from baseline

- Day 190 absolute change in FSHD-HI mobility and ambulation subscale score from baseline
  - To be done only for the “Knee Extension MRC-MMT Grade” and “Ankle Dorsiflexion MRC-MMT Grade” subgroups
- Day 190 absolute change in FSHD-HI activity limitation subscale score from baseline
  - To be done only for the “Knee Extension MRC-MMT Grade”, “Elbow Flexion MRC-MMT Grade”, and “Ankle Dorsiflexion MRC-MMT Grade” subgroups.

Subgroup analyses will be performed using similar ANCOVA models described in previous sections for each subgroup category provided that the sample size is at least 4 within each muscle. Because of the reduced sample size within each subgroup category, it is not planned to include MRC-MMT GRADE CATEGORY into such models. For each subgroup category, the treatment effect will be estimated and tested using a 0.1 (two-sided) significance level with the corresponding 90% confidence interval separately for TA and BB. Bar charts of the least squares mean estimates ( $\pm$  SEM) for each of the treatment groups will be provided for the individual muscle.

For purposes of this study, findings of subgroup analyses are considered to yield hypothesis generating statements for future study. It is not planned to control the overall type-1 error.

Additional analyses may be performed as appropriate.

Multiple imputations will be performed for missing data using the same approach outlined in [Section 4.7.2.2](#) or the parameter of interest.

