#### 4.1.1. Sample Size Determination

There was no formal sample size calculation for Part 1. Six patients in each cohort will provide sufficient data to evaluate safety and a preliminary assessment of changes in muscle volume and muscle strength.

The sample size calculation for Part 2 is based upon the percent change from baseline in total muscle volume of the injected TA muscle 3 weeks after the last dose. A 10% difference between ACE-083-treated and placebo groups in the percent change in total muscle volume from baseline is considered to be clinically meaningful. The standard deviation (SD) is assumed to be approximately 9% for each group, based on preliminary MRI data for the ACE-083-treated side from the initial TA cohort in Part 1. Similar assumptions apply for the treatment of the BB muscle.

Assuming a 2-sided type I error rate of 0.10, a 10% difference in percent change from baseline between ACE-083-treated and placebo groups in total muscle volume, a standard deviation of 9% for each group, and a 1:1 randomization, 83% power is achieved with a total sample size of 24 for the TA muscle (12 active, 12 placebo), based on a standard t-test.

In addition, this sample size also provides 83% power to detect a 10% difference in 6-minute walk test distance, based on a similar estimated SD of 9% and a 2-sided type 1 error rate of 0.10.

In order to account for dropouts (up to 15%), 28 patients will be randomized to study treatment for each muscle (14 active, 14 placebo) to ensure that at least 12 patients per treatment group complete the double-blind treatment period.

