##### **Primary Efficacy Analysis (Double-Blind Phase)**

###### **MRI: Total Muscle Volume**

Individual total muscle volume data will be listed. Descriptive statistics will be provided by treatment group and scheduled time for raw data and changes from baseline (absolute and percent change). Absolute and percent changes from baseline will be provided for each side (left and right) as well as the average of the absolute change and average of the percent change for the left and right sides. This will be done for the double-blind, placebo-controlled component as well as for the open-label component.

For the double-blind component, the plot of mean ( $\pm$  SEM) for the average of left and right side percent change in total muscle volume from baseline by scheduled day and treatment group for each muscle group (BB and TA) during the double-blind period as well as during the open-label extension period will be provided.

For the double-blind component, an ANCOVA model will be fitted in order to assess the effect of ACE-083 on the Day 190 average percent change from baseline in total muscle volume for the left and right sides. Covariates to be included in the model are MUSCLE, TREATMENT, BASELINE, MRC-MMT GRADE CATEGORY, MUSCLE\*TREATMENT, and BASELINE\*MUSCLE where:

- MUSCLE represents the muscle treated (BB or TA)
- TREATMENT represents the treatment group (ACE-083 or placebo)
- BASELINE represents the baseline total muscle volume (average of left and right sides)
- MRC-MMT GRADE CATEGORY represents the randomization stratification factor (3 to 4- or 4- to 4+)
- MUSCLE\*TREATMENT represents the muscle-by-treatment interaction
- BASELINE\*MUSCLE represents the baseline-by-muscle interaction

The effect of ACE-083 on the percent change in TMV from baseline of the injected TA or BB at Day 190 versus placebo will be estimated using the ANCOVA model described above and tested using a 0.1 significance level (2-sided) separately for TA and BB. The least squares mean estimate along with the corresponding 90% confidence interval will be provided separately for TA and BB. In addition, the 95% confidence interval will also be provided as well as a bar chart

of the least squares mean estimates ( $\pm$  SEM) for each of the treatment groups separately for TA and BB.

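### The subgroup plan tests treatment within each category but never estimates the difference in effect between categories, which is the quantity a subgroup hypothesis rests on

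*SAP*

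**What the plan says.** SAP 4.7.2.4 lists eight two-category factors; seven apply to TA and six to BB. The method is given as "Subgroup analyses will be performed using similar ANCOVA models described in previous sections for each subgroup category", subject to a size condition: "for each subgroup category provided that the sample size is at least 4 within each muscle". In each category the effect is estimated and tested: "For each subgroup category, the treatment effect will be estimated and tested using a 0.1 (two-sided) significance level". A 90% CI is given with each estimate, separately for TA and BB, and bar charts of the treatment-group means are drawn. MRC-MMT grade category is left out of these models because the categories are small.

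Two factors are split at the median: "Note that the median will be determined separately for BB and TA patients". The others use fixed cut-points or existing categories, so their splits may be uneven.

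For total muscle volume the parent model is described as follows: "Covariates to be included in the model are MUSCLE, TREATMENT, BASELINE, MRC-MMT GRADE CATEGORY", together with muscle-by-treatment and baseline-by-muscle terms. None of the parent models for the subgroup endpoints has a treatment-by-subgroup term. The section calls the findings hypothesis generating and says that overall type I error is not controlled.

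**The concern.** A subgroup hypothesis says that the drug works better in one kind of patient than in another. The evidence for it is the difference between the two category effects, with its uncertainty. The plan yields two effects and two p-values for each factor, and leaves the comparison to the reader's eye. With 6 or 7 patients per arm in a category, each test has moderate power. Identical true effects will then often give one p-value below 0.1 and one above it. That pattern is easily taken for differential response, and the bar charts would show it without the contrast that puts it in proportion. At stake is the quality of the hypotheses that the section says it will generate for later studies.

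**Working it through.** **Inputs, all from SAP 4.1.1 unless noted.** "Assuming a 2-sided type I error rate of 0.10, a 10% difference in percent change from baseline"; "a standard deviation of 9% for each group, and a 1:1 randomization"; 12 completers per arm per muscle from 14 randomized per arm; stated power 83% by t-test. The subgroup alpha of 0.10 two-sided and the minimum category of 4 come from SAP 4.7.2.4.

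**Formula.** With n per arm, the noncentrality is 10 / (9 × √(2/n)). Power p comes from the noncentral t with 2n − 2 degrees of freedom at two-sided 0.10.

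**Reproducing the plan's figure.** For n = 12 the noncentrality is 10 / (9 × 0.408) = 2.72 on 22 df. Power is 83.9%, in line with the stated 83%.

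**Even split, same true effect of 10 in both categories.** The probability that exactly one category is significant is 2p(1 − p).

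- 12 per arm split into 6 and 6: p = 55.9%; 2 × 0.559 × 0.441 = 49%. Both are significant in 31% and neither in 19%. Simulation also gave 49%.
- 14 per arm split into 7 and 7 (no losses): p = 62.4%; 2 × 0.624 × 0.376 = 47%.

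**Uneven splits of 24 completers.** The probability is pₐ(1 − p_b) + p_b(1 − pₐ).

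| Per arm in the two categories | Power in each | Exactly one significant |
|---|---|---|
| 5 and 7 | 48.5%, 62.4% | 50% |
| 4 and 8 | 40.2%, 68.0% | 54% |
| 3 and 9 | 30.8%, 72.9% | 59% |
| 2 and 10 (smallest category allowed, 4 patients) | 20.0%, 77.2% | 66% |

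**Sensitivity to the common effect, 6 per arm per category.** True effects of 0, 5, 8, 12 and 15 give 18%, 36%, 49%, 43% and 25%.

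**Sensitivity to the model.** The parent model for total muscle volume covers both muscles. With residual df pooled across muscles (18 for 6 per arm, 22 for 7 per arm), exactly one is significant in 49% and 46%.

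**The alternative.** The difference between two category effects has standard error 9 × √(4/n), with n per cell.

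- n = 6: SE 7.35, 20 df, 90% half-width 1.725 × 7.35 = 12.7 points.
- n = 7: SE 6.80, 24 df, 90% half-width 1.711 × 6.80 = 11.6 points.
- False-positive rate when the effects are identical: 10% by construction (9.5% simulated).
- Power for a 10-point difference in effects: 37% (n = 6) or 42% (n = 7). For a 20-point difference: 84% or 89%.

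**The case against.** The plan is open about its limits: it labels the results hypothesis generating and disclaims type I error control. It already gives a 90% CI in every category, so wide and overlapping intervals would be visible, and a reader could derive the difference and its standard error from the two estimates. The interaction is itself poorly powered. All of this is true, and it keeps the priority modest. It does not supply the missing contrast. The label answers a question about multiplicity, and low power is a reason to show the interval for the difference.

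Three stronger readings are tempting and should be set aside.

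- A reader might infer that the sponsor will declare a responder group whenever one category is significant and the other is not, or will select future patients that way. The SAP states no such rule; it speaks only of hypotheses for future study.
- A reader might infer that separate category models always lose precision by estimating residual variance from half the patients. For the MRI and FSHD-HI endpoints the parent models combine both muscles. For a factor shared by both muscles, an evenly split category model with no losses has about 28 patients and 6 parameters (22 df). A single-muscle interaction model has 28 patients and 5 parameters (23 df). The penalty there is negligible.
- A reader might count the category-level tests and cite the nominal positives expected under no effect. That is a multiplicity matter which the SAP discloses. It does not follow from the missing contrast, and interaction tests would share it.

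**Conclusion.** The concern holds as a gap in an exploratory section. The plan does not estimate the difference in effect between categories. With identical true effects at the design values, exactly one of two categories is significant in about half of trials: 47% to 49% for even splits and 50% to 66% for the uneven splits checked. An interaction test would flag 10%.

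The figures assume normal outcomes, equal SD, arms balanced within categories and no variance reduction from the baseline covariate, whose correlation with outcome is not given. They apply to total muscle volume. The SAP gives a comparable SD for only one other endpoint, 6-minute walk distance. The documents do not support the inference that the primary analysis or any decision rule is compromised.

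**What to change.** For each factor other than dose per contractile muscle mass, add SUBGROUP and the treatment-by-subgroup term to the endpoint's ANCOVA. Estimate the contrast within each muscle, either by fitting the muscles separately or by adding the matching muscle terms to the joint models. Keep the endpoint's other covariates: BASELINE, and HEIGHT for 6MWD and the 10-meter walk/run. Report the difference in treatment effect between categories with its 90% CI as the main subgroup result. Show the category effects with CIs beside it, and state that one significant and one non-significant category will not be read as differential response.

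Dose per contractile muscle mass needs separate handling. SAP 4.4.2 derives it from the ACE-083 dose injected, which placebo patients do not have. Define the factor for placebo patients explicitly, or leave it out of the interaction analysis.

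The imputation models referred to in 4.7.2.4 contain no subgroup terms. The SAP should say whether they will be extended for these analyses.

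The cost is SAP wording and some programming before database lock, with no new data. The drawback is a wide interval and low power, as shown above.
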